Protocol Title: Understanding perceived access and receipt of gender-affirming treatments among transgender Veterans

Funding Agency: VA Health Services and Research Development (IIR 22-201)

Principal Investigator: [name]

Version 7

August 13, 2025

NCT06615401

Abstract

Background: Transgender people experience discord between their gender identity and birth sex, defined as gender dysphoria. Gender-affirming treatments (GATs) are medically necessary treatments to reduce gender dysphoria. However, among transgender Veterans (trans Vets) who desire GATs, not much is known about barriers and facilitators to accessing and receiving GATs in VA and VA Community Care (CC). To ensure effective and equitable GAT access for trans Vets, it is critical to understand: [1] GATs trans Vets receive and where they receive them, [2] barriers, including social determinants of health (SDOH) barriers that are highly prevalent among trans Vets, and facilitators associated with desired GAT receipt in VA and CC, [3] how barriers and facilitators influence GAT access and desire, and [4] how to improve GAT access in VA and CC.

Objectives: We propose a sequential explanatory mixed method study whose aims are to:

Aim 1. Characterize the GATs received by trans Vets in VA and/or CC (VA/CC)

Aim 2. Identify barriers and facilitators associated with desired GAT receipt in VA and CC

Aim 3: Understand trans Vet experiences related to GAT access in VA and CC.

Research Design: Aim 1: We will expand our VA cohort of 9,608 trans Vets (IIR 17-238) from 2006-18 to the data available at the time of funding. We will add CC data to determine the types of GATs received by trans Vets in VA and/or CC. Aim 2: We will survey a national sample of trans Vets identified from Aim 1. Among trans Vets who desire GATs, we will determine SDOH barriers, other barriers, and facilitators associated with desired GAT receipt. Among trans Vets who did not desire GATs, we will determine reasons for not wanting GATs. Aim 3: From Aim 2 participants, we will recruit a purposive sample of trans Vets who received all desired GAT(s), who received some desired GAT(s), and who received no desired GAT(s). We will also recruit a national sample of LGBTQ+ Veteran Care Coordinators. We will seek to understand experiences and perspectives on GAT access in VA and CC, how SDOH barriers, other barriers, and facilitators influence GAT access and desire, and how to improve GAT access in VA and CC. Informed by study findings and in partnership with our Stakeholder Advisory Group, we will develop patient-centered implementation strategies to mitigate barriers and enhance facilitators to improve GAT access in VA and CC.

Findings/Progress to Date: No findings to date.

Relevance to VA Mission

This study addresses the 2022 HSR&D priority areas of Access to Care, Health Equity/SDOH, MISSION Act, and research gap of underserved LGBTQ+ Veterans. It is also a high priority for our operational partners in VA LGBTQ+ Health Program, Pharmacy Benefits Management, Office of Integrated Veteran Care, and Office of Mental Health and Suicide Prevention. Knowledge gained from this study will ensure that GAT delivery in the VA is patient-centered and is responsive to the lived realities and needs of trans Vets.

List of Abbreviations

- (CC) VA Community Care
- (CDA) Career Development Awardee
- (CDW) Corporate Data Warehouse
- (GAT) Gender-affirming treatment
- (HSR&D) Health Services Research & Development
- (IIR) Investigator Initiated Research
- (LGBTQ+) Lesbian, gay, bisexual, transgender, queer (or questioning) and other identities
- (LGBTQ+ VCC) LGBTQ+ Veteran Care Coordinator
- (Trans Vets) Transgender Veterans
- (TGD) Transgender and gender diverse Veterans
- (VA) Department of Veterans Affairs
- (VAMC) Veteran Affairs Medical Center
- (VCC) Veteran Care Coordinators
- (VINCI) VA Informatics and Computing Infrastructure

Contents

Protocol Title:	5

2.0 Introduction

Transgender people commonly experience gender dysphoria defined as distress due to discord between their gender identity and birth sex.¹ The number of transgender Veterans (trans Vets) with gender dysphoria increased ~7-fold from 1,406 in 2006 to 9,608 in 2018 in VA.² Compared to non-trans Vets, trans Vets with gender dysphoria have > 2-fold hazard of suicide mortality.³ Gender-affirming treatments (GATs; e.g. surgery, hormones)⁴ are evidence-based treatments to reduce gender dysphoria, improve mental health and quality of life in trans people.⁵⁻⁹ Receipt of hormones and/or surgery reduced suicidal ideation by 62% among trans people¹⁰ with similar findings noted among trans Vets.¹¹ GATs are medically necessary for gender dysphoria.^{4,12-14} However, not much is known about the barriers and facilitators to accessing and receiving GATs in VA and VA Community Care (i.e., care paid for by the VA in the community)¹⁵ among trans Vets who desire GATs.

Barriers to receipt of GATs reported in a single-site VA study included delays in GAT receipt, need to travel for GATs, lack of clinician competency on trans health, discrimination, violence and lack of patient knowledge about VA GAT coverage.¹⁶ Additional barriers suggested by non-VA studies, include low income, housing instability, and cost of GATs.¹⁷⁻²¹ Barriers to GATs thus, reflect social determinants of health (SDOH) barriers (e.g. discrimination)²² and other barriers (e.g. lack of patient knowledge about GAT coverage). In our ongoing IIR 17-238 using VA data, trans Vets with SDOH barriers, including housing instability, financial strain, and violence were 38% less likely to receive hormones than those without SDOH barriers.²³ Trans Vets frequently experience SDOH barriers, with 28% experiencing housing instability, 31% unemployment, and 19.5% violence.²⁴ Thus, targeting SDOH barriers that are especially salient in the lives of trans Vets along with other barriers are promising approaches to improving GAT access and receipt in VA and VA Community Care (CC).

However, little is known about which GATs trans Vets receive and where they receive them, which is critical to understand how VA and CC are balanced in terms of delivering GATs. Also, among trans Vets who desire GATs, not much is known about the barriers and facilitators that influence receipt of desired GATs in VA and CC. Further, we lack an understanding of trans Vets experiences related to GAT access in VA and CC, how barriers and facilitators influence GAT access and desire and how GAT access might be improved in VA and CC.

3.0 Objectives

Specific Aims

Aim 1. Characterize the GATs received by trans Vets in VA and/or CC. We will expand our VA cohort of 9,608 trans Vets² (IIR 17-238) from 2006-18 to the most recent year of data available at the time of funding. We will then add CC data to characterize the GATs received by trans Vets in VA only, CC only, and VA and/or CC. We will also expand our ongoing work on receipt of hormone therapy in VA to examine it in CC as well.

Aim 2. Identify barriers and facilitators associated with receipt of desired GATs in VA and CC. We will survey a national sample of trans Vets with new gender dysphoria diagnoses identified from Aim 1. Among trans Vets who desire GATs, we will determine SDOH barriers, other barriers, and facilitators associated with receipt of desired GATs in VA and/or CC. Among trans Vets who did not desire GATs, we will determine reasons for not wanting GATs to

distinguish between trans Vets who truly do not desire GAT (e.g., due to nonbinary identity) and trans Vets who may desire GATs if certain barriers to GAT access could be addressed.

^{5.0} **Aim 3. Understand trans Vet experiences related to GAT access in VA and CC.** From Aim 2, we will recruit a purposive sample of trans Vets who received all desired GAT(s), some desired GAT(s), and no desired GAT(s). We will also recruit a national sample of LGBTQ+ Veteran Care Coordinators, who are point persons for trans Vets at VA sites.²⁷ Participant interviews will explore experiences and perspectives on GAT access in VA and CC, how SDOH and other barriers influence GAT access and desire, and suggestions for improving GAT access.

Relevance

Informed by study findings and in partnership with our Stakeholder Advisory Group, we will develop patient-centered implementation strategies to improve GAT access. We will deploy these strategies in a follow-up hybrid implementation effectiveness study to mitigate barriers and enhance facilitators to improve GAT access in VA and CC and promote trans health equity. This work addresses HSR&D priorities of health equity/SDOH, access to care, MISSION Act, underserved LGBTQ+ Veterans; and is informed by our ongoing IIR 17-238.

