5.0 Study Procedures

5.1 Study Design

This is an observational multi-method cross-sectional study with transgender Veterans that will identify barriers and facilitators associated with GAT receipt among trans Vets who desire GATs. We will also identify patient-centered strategies to address barriers and enhance facilitators to improve GAT access. The proposed study will use a mixed-methods design, with three aims. We begin with obtaining national VA data to provide a foundational lay of the land on the GATs received by trans Vets in VA and/or CC (database Aim 1). Next, using a national cross-sectional survey, we will identify barriers and facilitators associated with receipt of desired GATs in VA and CC (survey Aim 2). Finally, by interviewing trans Vets and LGBTQ+ VCCs, we

will understand experiences and perspectives on GAT access in VA and CC, and how to improve this access in VA and CC (qualitative Aim 3).

Database Aim 1: We will expand our VA cohort of 9,608 trans Vets (IIR 17-238) from 2006-18 to the data available at the time of funding. We will add CC data to determine the types of GATs received by trans Vets in VA and/or CC. Aim 1 of the study will consist of all Veterans with documentation of a gender dysphoria (GD) diagnosis code in the VA or in CC from 1999 to the current year for which VA and CC data is available.

Survey Aim 2: We will survey a national sample of up to 1,500 trans Vets with a documentation of a gender dysphoria (GD) diagnoses identified from Aim 1 in the VA or CC in the past 2 years at the time of funding. Among trans Vets who desire GATs, we will determine barriers, and facilitators associated with desired GAT receipt. Among trans Vets who did not desire GATs, we will determine reasons for not wanting GATs. Veterans will be invited by postal mail, email, and phone to participate in a single survey. Similar to our pilot testing recruitment, we will also advertise the survey on VA's LGBTQ+ Health Office website and we will work on recruitment with LGBTQ+ Veteran Care Coordinators (VCCs). Veterans will be encouraged to complete the survey online but will have the option to complete the survey by phone or mail if desired. Data from the survey will be linked to CDW data (available through VINCI) via a study ID, and the crosswalk file will be stored in a separate secure file and will only be accessible to study team members.

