We anticipate inviting approximately 10,000 trans Vets with a gender dysphoria diagnosis and/or self-reported gender identity as transgender and gender diverse to participate in the national survey and expect up to 1,500 will enroll and complete the survey. Recruitment for the national survey will consist of direct outreach to prospective research participants identified in Aim 1 through a mailed or emailed recruitment letter and Information Statement alerting Veterans about the survey, providing details about the individuals' rights as a research participant and inviting them to participate in the study. The letter will explain that the survey is entirely voluntary and that if they choose not to participate or to end the survey prior to completion, there will be no penalties or loss of VA benefits. The communication will make clear that the survey responses are confidential and that the Veteran's name or any other personally identifying information will not be used in any report of the survey results. The IRB's telephone number will be provided as a means for the potential participant to use to verify that the study constitutes VA research. Additionally, the study project manager's telephone number will be provided for the Veteran to call with questions about the study or if they wish to opt out of the study.

Veterans will be contacted as follows:

Contact	Method	Specifics
---------	--------	-----------

Contact 1	First Letter	All Veterans with a gender dysphoria diagnosis in the past 2 years and/or self-identified gender identity as transgender and gender diverse will be sent a recruitment letter via mail and/or email inviting them to participate in the study and offering the ability to opt-out, complete the survey online (either through mobile device, tablet or desktop), call in to the study project manager's number to complete the survey with the study manager or request that a paper survey is mailed to them.
Contact 2	Second letter	A second letter will be sent via mail and/or email approximately 10 days after the first letter.
Contact 3	Reminder Postcard	Approximately ten to twelve days after the second letter, we will send a reminder postcard and/or letter and/or email reinforcing basic information provided earlier and directing people to the website or to call the study project manager's number to complete the survey.

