5.4 Inclusion/Exclusion Criteria

Inclusion criteria for database aim 1: Aim 1 of the study will consist of all Veterans with documentation of a gender dysphoria/gender identity disorder diagnosis code in the VA or in CC from 1999 to the current year for which VA and CC data is available. We will also request a sample of Veterans without a gender dysphoria/gender identity disorder diagnosis code in VA and/or CC or otherwise not identified as TGD through self-identified gender identity (non-TGD) to compare our TGD cohort on variables such as demographics, health condition, utilization, etc.

Inclusion criteria for survey aim 2: For survey aim 2, we will identify Veterans with a documentation of a gender dysphoria/gender identity disorder diagnoses in the VA or CC in the past 2 years at the time of funding.

Inclusion criteria for qualitative aim 3: From survey aim 2, we will recruit a purposive sample of ~70 trans Vets. We will also recruit ~ 20 LGBTQ+ VCCs.

There are no exclusion criteria for any of the aims to allow participation from the full range of trans Vets.

Rational for Involvement of Vulnerable Populations

We will not exclude VA employees, students, pregnant people, economically and/or educationally disadvantaged persons, or terminally ill patients. These participants will not be specifically targeted for recruitment; if participants happen to fall into these subcategories, it would be coincidental. The aim of the study is to examine the health of transgender Veterans – thus, exclusion criteria are minimal to approximate as generalizable a sample as possible. The study procedures would not be of elevated risk to these subpopulations as compared to the general population.

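### The Aim 2 survey population is defined in conflicting ways (new diagnoses, any diagnosis in 2 years, or self-identified), and time since first diagnosis is not named in the analysis

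*Combined protocol and SAP*

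**What the plan says.** The combined protocol and SAP describes the Aim 2 survey population in five places, all current text.

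- **3.0 Objectives, Aim 2:** "We will survey a national sample of trans Vets with new gender dysphoria diagnoses identified from Aim 1". The word new is not defined.
- **Abstract, Research Design:** "We will survey a national sample of trans Vets identified from Aim 1". No condition on new diagnosis.
- **5.1 Study Design, Survey Aim 2:** "up to 1,500 trans Vets with a documentation of a gender dysphoria (GD) diagnoses identified from Aim 1", within a 2-year window at the time of funding. It also plans website advertising and work with care coordinators.
- **5.4 Inclusion/Exclusion Criteria:** "we will identify Veterans with a documentation of a gender dysphoria/gender identity disorder diagnoses in the VA or CC in the past 2 years". No first-code condition and no code-free look-back. No aim has exclusion criteria; the stated purpose is to admit the full range of transgender Veterans.
- **5.2 Recruitment Methods, Contact 1:** "All Veterans with a gender dysphoria diagnosis in the past 2 years and/or self-identified gender identity as transgender and gender diverse". The roughly 10,000 invitations and up to 1,500 completers are stated for this wider group.

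Section 5.2 also adds partner distribution lists and, if enrollment is low, advertising, service organizations and snowball recruitment. No diagnosis condition is stated for these routes.

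In section 5.6, the models adjust for covariates such as age, race/ethnicity and gender identity. The descriptive subgroups are age, race/ethnicity, gender identity and region. Time since first diagnosis appears in neither list.

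**The concern.** The objective describes an incident population, while the eligibility rule and the contact schedule describe prevalent ones. These can give different answers to the Aim 2 question.

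The dependent variables in the primary analyses include receipt of GATs and the degree of receipt of desired GATs. A Veteran first diagnosed many years ago has had longer to obtain every desired treatment than one diagnosed last year. Time since first diagnosis is therefore a likely determinant of the outcome, and it may also be related to barriers such as housing, employment or knowledge of coverage. If it is neither fixed by eligibility nor handled in the analysis, the associations average over an unknown mix of durations and may be confounded by duration.

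The problem carries into Aim 3, which samples survey respondents by whether they received all, some or none of their desired treatments. The diversity factors listed for that sample also omit time since diagnosis.

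**Working it through.** **1. Does mixing follow from the text?** Take a Veteran first coded in 2005 and coded again inside the 2-year window.

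| Source | Requirement | Admitted? |
|---|---|---|
| 3.0 Objectives | new diagnosis | No |
| 5.1 and 5.4 | any documented diagnosis in 2 years | Yes |
| 5.2, Contact 1 | diagnosis in 2 years and/or self-identified | Yes |

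A second Veteran, self-identified but with no code in the window, is outside 3.0, 5.1 and 5.4 but is invited under 5.2. There are thus three different frames. Mixing of new and long-standing patients follows without any numerical assumption.

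**2. The plan's own figures.** The implied yield is 1,500 / 10,000 = 15%. The 1,500 has no stated power, precision or response-rate basis, so it cannot be reproduced. The growth statement in 2.0 Introduction does reproduce: 9,608 / 1,406 = 6.83, about 7-fold.

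**3. How large might a newly diagnosed group be? (Illustration.)** Assumptions: the counts 1,406 (2006) and 9,608 (2018) are cumulative, as the abstract's description of a 2006-18 cohort suggests; growth continues; yield is 15%. The documents give no calendar end for the window, so several years are shown.

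- Linear growth: (9,608 − 1,406) / 12 = 683.5 per year. Two years give 1,367, and 0.15 × 1,367 = about 205 completers, whatever the end year.
- Constant rate: (9,608 / 1,406)^(1/12) = 1.174, or 17.4% per year. New diagnoses in two years = total × (1 − 1.174⁻²), computed with the unrounded rate:

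| Window ends | Cumulative total | New in 2 years | Completers at 15% |
|---|---|---|---|
| 2018 | 9,608 | 2,633 | 395 |
| 2022 | 18,233 | 4,997 | 750 |
| 2023 | 21,399 | 5,865 | 880 |
| 2024 | 25,116 | 6,884 | 1,033 |

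None of these reaches 10,000 invitees or 1,500 completers. For precision, the 95% half-width for a proportion of 0.5 is 1.96 × √(0.25/n): 2.5 percentage points at n = 1,500, 3.3 at 880 and 6.8 at 205.

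**4. Does entry by recent code distort the treated share?** Suppose long-standing patients enter only by a code, with at least one code in 2 years having probability 1 − exp(−2 × rate), and suppose 50% are truly treated. All rates are assumed.

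| Codes per year, treated vs untreated | Entry probability | Treated share in sample |
|---|---|---|
| 1 vs 1 | 0.86 vs 0.86 | 50% |
| 1 vs 0.5 | 0.86 vs 0.63 | 58% |
| 2 vs 0.5 | 0.98 vs 0.63 | 61% |
| 2 vs 0.25 | 0.98 vs 0.39 | 71% |

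The result ranges from no distortion to 21 percentage points, depending wholly on rates that the documents do not give.

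**The case against.** The strongest reply is that the word new appears once, undefined, against four other descriptions that omit it, and that section 5.4 says the intent is to admit the full range of transgender Veterans. Deleting one word might then be the whole reconciliation. This stands in part: deletion would align the objective with the study design. It would not settle the difference between sections 5.4 and 5.2, and it would leave an outcome that plausibly depends on duration with no duration variable named. The covariate list is open-ended, so the variable could still be added, but nothing commits the analysts to it.

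Three stronger readings are tempting and should not be drawn.

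- A reader might infer that the 2-year rule over-selects Veterans still in treatment. The documents give no coding rates by treatment status, and a code shows contact with care, not receipt of treatment. Veterans who have completed treatment could also stop generating codes, so even the direction is open.
- A reader might infer that long-standing patients who disengaged are never invited. Section 5.2 also invites self-identified Veterans and has routes with no recent-code condition.
- A reader might infer that barriers are measured long after receipt. The instrument and its recall periods are not in the documents, and section 5.6 speaks of barriers met in obtaining treatment.

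It is also fair to say that the growth figures are VA counts extrapolated beyond 2018, so they cannot establish the actual share of new cases. The 10,000 includes self-identified Veterans and is not a count of recent diagnoses.

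**Conclusion.** The concern holds as a conflict over who Aim 2 studies. The objective names newly diagnosed Veterans, sections 5.1 and 5.4 admit any documented diagnosis in 2 years, and section 5.2 invites a wider group again. Under the current text, results on receipt of desired GATs would describe a mixture of new and long-standing patients, with no named step to separate them. This rests on the wording alone.

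The size is not determined. The range of about 205 to 1,030 newly diagnosed completers depends on reading the counts as cumulative, on continued growth, on a window ending no later than 2024 and on a 15% yield. It shows only that the choice of population could materially change the sample available for the stated objective. Selection through recent codes may favour Veterans in contact with care, but its direction and size are not established.

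**What to change.** 1. Reconcile the abstract and sections 3.0, 5.1, 5.2 and 5.4 so that they state one Aim 2 population. Either drop the word new from the objective, or define it as a first-ever VA or Community Care code inside the 2-year window, using the look-back to 1999 in the Aim 1 data. Say explicitly whether self-identified Veterans without a recent code belong to the population.
2. Keep the wide invitation list. Derive time since first diagnosis from the Aim 1 data and the planned linkage to the VA Corporate Data Warehouse.
3. In section 5.6, include that variable in the Aim 2 models, with a separate category for respondents with no code, and report new and long-standing strata separately.
4. State in section 5.2 that the 10,000 and 1,500 figures describe the frame of recent diagnosis and/or self-identification, not newly diagnosed Veterans.

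The cost is wording changes and one derived variable, with no new data collection. The newly diagnosed stratum will be smaller than the full sample, with wider intervals than 1,500 completers would give. The derived date marks the first code in VA or Community Care records, so a diagnosis made elsewhere earlier would be missed, and duration stays undefined for respondents with no code. Both limits should be stated.
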